8.4.3.2 Additional Long-term Safety Assessment

Due to the randomized withdrawal design, additional safety analyses will be performed up to Week 32 along with modified analyses performed at Week 52 to account for the randomized withdrawal. These assessments of safety will be based on the safety parameters already described (Section 8.4.3).

Selected safety analyses performed during the ST and LT periods (Section 8.4.3.1) will also be conducted during the treatment period up to Week 32 to account for randomized withdrawal. This will include analyses of AEs, hypoglycemia events, DKA events, and clinical laboratory marked abnormalities. All safety data will be summarized by treatment group based on the treatment received (dapagliflozin/saxagliptin/placebo) using the Treated Subjects Data Set.

To assess the effects of dapagliflozin (or saxagliptin) versus placebo on safety endpoints for subjects on background medication (i.e., excluding subjects re-randomized to withdraw from metformin) a weighted analysis will be conducted for select safety parameters using the Treated Subjects Data Set using the original randomized groups.

Dapagliflozin (or saxagliptin) subjects who went through the last randomization and withdrew metformin will get a weight of zero and those randomized to stay on metformin will get a weight of 2.

Placebo subjects randomized to withdraw metformin and switched to active treatment will get a weight of zero. Placebo subjects randomized to stay on metformin will get a weight of 3. All other subjects will get a weight of 1.

Additional safety analyses will be performed on the Treated Subjects Data Set on AEs, DKA events, hypoglycemia events, and clinical laboratory marked abnormalities during the ST and LT treatment periods to compare safety endpoints per treatment received at the time of the event.

For placebo subjects re-randomized to switch to dapagliflozin (or saxagliptin), events and clinical laboratory marked abnormalities will be classified in the placebo group up to the beginning of the randomized withdrawal period and in the dapagliflozin (or saxagliptin) group during the randomized withdrawal period.

Furthermore, as the length of exposure in the treatment received following the re-randomization withdrawal process may be shorter for the subjects who switch from placebo to dapagliflozin (or saxagliptin); these events and marked abnormalities analyses will report incidence rates adjusted for exposure time.

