4.7 Safety

Safety analyses will be conducted for the ST, ST+LT, and randomised withdrawal (as applicable) periods. An additional safety analysis will be provided for the post-study visit at Week 104, to summarise assessments of measures of growth and maturity by treatment group. Summaries will be based on the Treated Subjects Data Set unless otherwise stated.

The primary analyses of safety will include data regardless of rescue medication initiation, unless otherwise specified. Additional sensitivity analyses on data collected prior to rescue will be performed for AEs and laboratory marked abnormalities.

Dapagliflozin and saxagliptin will be summarised separately. Both low-dose and high-dose dapagliflozin/saxagliptin groups will be combined for dapagliflozin/saxagliptin to provide the

safety summary for overall dapagliflozin/saxagliptin compared to placebo. A common placebo group will be included in each summary.

Additional analyses will be performed during the ST+LT period to account for the randomised withdrawal design:

- Safety analyses conducted during the ST+LT period will also be conducted during the treatment period up to Week 32.
- Safety analyses conducted during the ST+LT period will also be conducted based on the treatment received at the time of the assessment to account for changes in treatment during the randomised withdrawal period (dapagliflozin/saxagliptin/placebo).
- Weighted analysis will be conducted for select safety parameters including adverse events, marked abnormal labs and ECGs using the original randomised groups to assess the effects of dapagliflozin (or saxagliptin) versus placebo on safety endpoints for subjects on background medication (i.e., excluding subjects re-randomised to withdraw from metformin).

The weight matrix denoted by W_3 is defined as follows:

$$W_3 = \text{Diag} \begin{bmatrix} \mathbf{0}_{1 \times \frac{rn}{2}} \\ \mathbf{2}_{1 \times \frac{rn}{2}} \\ \mathbf{1}_{1 \times (1-r)n} \\ \mathbf{0}_{1 \times \frac{2rn}{3}} \\ \mathbf{3}_{1 \times \frac{rn}{3}} \\ \mathbf{1}_{1 \times (1-r)n} \end{bmatrix}$$

where r is the proportion of subjects eligible for the third randomisation and n is the number of subjects within an arm.

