4.7.2.2 Adjudicated Diabetic ketoacidosis (DKA)

All suspected DKA events sent for adjudication will be included in summaries for the ST, ST+LT and randomised withdrawal periods if their onset falls between the start of IP treatment and the cut-off dates defined for each period in [Table 8](#).

The proportion of subjects with suspected DKA events sent for adjudication, regardless of rescue medication initiation, will be tabulated by treatment group per adjudication category (definite DKA, probable DKA, possible DKA, not DKA) for the ST, ST+LT and randomised withdrawal periods. The proportion of subjects with suspected DKA events sent for adjudication leading to discontinuation per adjudication category will also be summarised for the ST+LT period. When summarising suspected DKA events leading to discontinuation of study medication, no upper cut-off day windows are applied.

Furthermore, suspected DKA events sent for adjudication will be summarised for the ST, ST+LT and randomised withdrawal periods by treatment group per adjudication category for number of subjects with each sign and symptom and separately, risk factors.

Suspected DKA events sent for adjudication will also be presented ST, ST+LT and randomised withdrawal periods by treatment group per adjudication category and preferred term. This analysis for the ST+LT period will be repeated for the subgroup of subjects on a stable baseline dose of metformin IR or XR (with or without insulin).

A listing of suspected DKA events sent for adjudication will be generated for adjudication results, signs and symptoms, and risk factors with an onset date/time from the start date/time for the ST+LT period. For the ST+LT + Week 104 period, the listing will include all data collected up to Week 104.

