5. INTERIM ANALYSES (NOT APPLICABLE)

6. CHANGES OF ANALYSIS FROM PROTOCOL

Table 12 Changes of analysis from protocol

Section of SAP Affected (If applicable)	Change	Rationale
Section 2.2.7	A PK analysis data set was defined in the SAP, but this isn't mentioned in the study protocol.	It is necessary to have an analysis set defined for the PK data.
Section 4.1.1	The definition of the withdrawal baseline differs between the study protocol and the SAP.	This change was made to align the withdrawal baseline with how we define dose at onset and how to handle scenarios where the randomisation was done on a different date to the main visit.
Section 4.1.10	Fisher's exact test is used instead of logistic regression where there are <5 responders per treatment group.	This analysis was not mentioned in the protocol.
Section 4.1.12	The "wash-out" imputation method is used where there is insufficient data from "retrieved drop-outs".	This analysis was not mentioned in the protocol.

Section of SAP Affected (If applicable)	Change	Rationale
Sections 4.4 and 4.5	The primary efficacy endpoint was updated to use overall treatment and the secondary efficacy endpoints were updated to follow the order/hierarchy of overall, followed by low-dose/high-dose regimen testing, followed by low-dose regimen.	This was due to protocol amendment #6.
Section 4.7.1.1	The protocol states that additional safety analyses will be performed on the Treated Subjects Data Sets on all DKA events but in the SAP, we only present the analysis for adjudicated DKA SAEs.	Additional analyses were only done on confirmed DKAs.
Section 4.10	It was decided that all the TFLs will be produced excluding data collected from Site 4910. In addition, a few analyses will be produced including subjects from Site 4910.	This was due to loss of access to the source data of subjects at Site 4910. This decision was made following investigation by AstraZeneca.
Appendix 8.13	The protocol states that “separate analyses will be performed for subjects respectively randomized to the dapagliflozin or saxagliptin group” while in the SAP, we combine the randomised withdrawal treatment into one analysis table.	Presenting the data this way was more informative.

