Last randomised/actual treatment		Disposition, Demographics, Safety
Dapagliflozin 10mg monotherapy	All subjects whose last randomised/actual treatment was dapagliflozin and the	

Treatment label	Explanation	Analysis purpose
	subject was randomised to withdraw background metformin	
Dapagliflozin 5mg or 10mg	All subjects whose last randomised/actual treatment was dapagliflozin and the subject remained on background metformin (if eligible for third randomisation)	
Saxagliptin 5mg monotherapy	All subjects whose last randomised/actual treatment was saxagliptin and the subject was randomised to withdraw background metformin	
Saxagliptin 2.5mg or 5mg	All subjects whose last randomised/actual treatment was saxagliptin and the subject remained on background metformin (if eligible for third randomisation)	
Placebo	All subjects whose last randomised/actual treatment was placebo and the subject remained on background metformin (if eligible for third randomisation)	
Dose at onset / actual dose and treatment taken		Dose at onset outputs: Safety (exposure, AEs, labs)
Dapagliflozin 5mg	All subjects on dapagliflozin 5mg per treatment assignments in Section 4.1.6	
Dapagliflozin 10mg	All subjects on dapagliflozin 10mg per treatment assignments in Section 4.1.6	
Total Dapagliflozin	All subjects who took Dapagliflozin based on all three randomisations	
Saxagliptin 2.5mg	All subjects on saxagliptin 2.5mg per treatment assignments in Section 4.1.6	

Treatment label	Explanation	Analysis purpose
Saxagliptin 5mg	All subjects on saxagliptin 5mg per treatment assignments in Section 4.1.6	
Total Saxagliptin	All subjects who took Saxagliptin based on all three randomisations	
Placebo	All subjects on placebo per treatment assignments in Section 4.1.6	
Highest dose taken in ST period		PK outputs
Dapagliflozin 5mg	All subjects whose highest actual dose in the ST period was dapagliflozin 5mg	
Dapagliflozin 10mg	All subjects whose highest actual dose in the ST period was dapagliflozin 10mg	
Saxagliptin 2.5mg	All subjects whose highest actual dose in the ST period was saxagliptin 2.5mg	
Saxagliptin 5mg	All subjects whose highest actual dose in the ST period was saxagliptin 5mg	

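### The 52-week DKA tables omit non-serious events by treatment at onset with exposure-adjusted rates, which the protocol requires, and the reason given for the omission does not fit it

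*SAP*

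**What the plan says.** Protocol 8.4.3.2 plans for children who change treatment at the third randomisation: "Additional safety analyses will be performed on the Treated Subjects Data Set on AEs, DKA events, hypoglycemia events, and clinical laboratory marked abnormalities" over the short-term and long-term periods, "to compare safety endpoints per treatment received at the time of the event". For a placebo child who switches, events count under placebo before the switch and under the active drug after it. Because exposure after the switch is short, "these events and marked abnormalities analyses will report incidence rates adjusted for exposure time". DKA is named separately from AEs, with no limit to serious events.

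The SAP treats DKA in several places:

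- Section 3.4.1 leaves DKA that is not an SAE out of the AE data; such events go on separate CRF pages (3.4.3.1).
- Section 4.7.2.2 has suspected DKA events sent for adjudication "tabulated by treatment group per adjudication category (definite DKA, probable DKA, possible DKA, not DKA) for the ST, ST+LT" and randomised-withdrawal periods.
- Section 4.7 makes a general commitment: "Safety analyses conducted during the ST+LT period will also be conducted based on the treatment received at the time of the assessment".
- Appendix 8.13 gives the scope of the by-dose-at-onset presentation as "Dose at onset outputs: Safety (exposure, AEs, labs").
- Table 12 (Section 6) declares a change from the protocol: "in the SAP, we only present the analysis for adjudicated DKA SAEs". The rationale is: "Additional analyses were only done on confirmed DKAs".

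**The concern.** The protocol describes DKA as a potential risk with SGLT-2 inhibitors (5.3.2), and its incidence over up to 52 weeks is a safety objective (1.3.3). Two of every three eligible placebo children move to active drug at Week 32 or 40, one of them to dapagliflozin 10 mg. A table by first treatment then carries dapagliflozin exposure, and any DKA that arises in it, in the placebo column. The misplacement can only raise the placebo count and lower the dapagliflozin count, so it tends to understate the drug's risk. The at-onset analysis in the protocol was meant to prevent this, and for non-serious DKA the SAP does not carry it through.

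**Working it through.** **Tracing a non-serious DKA that starts on dapagliflozin after a switch from placebo**

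| SAP output | Is the event there? | Under which treatment? | Exposure-adjusted rate? |
|---|---|---|---|
| At-onset AE and SAE tables (4.7.1.1, 4.7.1.3) | No; only DKA that is an SAE enters (3.4.1) | n/a | n/a |
| ST+LT DKA tables (4.7.2.2, Table 24) | Yes | Placebo, by first treatment (2.1, 2.2.5, 8.13) | No |
| Randomised-withdrawal DKA tables (4.7.2.2, Table 24) | Yes | Dapagliflozin | No; proportions for that period only |
| By-subject DKA listing (4.7.2.2, sorted as in 4.1.7) | Yes | Traceable through the third randomisation | No |

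Table 24 has a row by treatment at onset for overall AEs, AEs by SOC and PT, SAEs and marked laboratory abnormalities. It has none for adjudicated DKA. No itemised ST+LT output therefore gives what Protocol 8.4.3.2 asks for.

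**The Table 12 rationale**

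The restriction is by seriousness; the reason offered is confirmation. Section 3.4.3.1 sets the adjudication categories (definite, probable, possible, not DKA) without reference to seriousness. A non-serious event can be adjudicated definite, so it is confirmed yet excluded. A serious event can be adjudicated not DKA. The reason does not lead to the restriction. The row also conflicts with the general sentence in Section 4.7, so a programmer cannot follow both for DKA.

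**Size**

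There is no plan figure to reproduce. From the documents: about 81 placebo children, a 1:1:1 split of eligible placebo children, switch at Week 32 or 40, treatment to Week 52. The share *r* of placebo children entering the third randomisation is not given and is assumed.

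- Children switched to dapagliflozin = 81 × *r* / 3. For *r* = 0.10: 2.7. For *r* = 0.40: 10.8.
- Time on dapagliflozin runs from 12 weeks (switch at Week 40) to 20 weeks (switch at Week 32). Low end: 2.7 × 12/52 = 0.62 patient-years. High end: 10.8 × 20/52 = 4.15 patient-years.
- Share of placebo time, taking 81 patient-years (81 children fully treated for 52 weeks): 0.62/81 = 0.8% to 4.15/81 = 5.1%.
- Lower case, *r* = 0.05: 81 × 0.05 / 3 = 1.35 children, and 1.35 × 12/52 = 0.31 to 1.35 × 20/52 = 0.52 patient-years. This is plausible because participation was optional for earlier recruits (Protocol 3.1) and some children passed Week 32/40 before the amendment was approved in their country (SAP 4.2).
- One affected child in the first-treatment table: 1/81 = 1.23 percentage points under placebo.
- The same event by treatment at onset, total dapagliflozin, also taking 81 patient-years for the original dapagliflozin arm: 100/(81 + 4.15) = 1.17 to 100/(81 + 0.62) = 1.23 per 100 patient-years.

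**The case against.** The departure is disclosed in Table 12, so nothing is hidden. No event is lost either. Serious DKA is re-attributed at onset, and the withdrawal-period tables put switched children under dapagliflozin against children re-randomised to stay on placebo with metformin. Over 12-20 weeks, proportions lose little against rates. Table 8 sets an up-to-Week-32 cut-off for non-serious DKA, which allows a comparison free of switching, and the listing covers every suspected event. The SAE definition is broad, so few DKA events may be non-serious. The Table 12 row cites only Section 4.7.1.1, where the DKA lines are indeed limited to SAEs, so it could be read alongside the general commitment in Section 4.7. Table specifications are kept in separate documents (SAP 4.1) and might include the missing table.

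Most of this stands as a limit on size, and the point is graded accordingly. It does not close the gap. None of these outputs gives the 52-week rate that the protocol specifies. A disclosed change still needs a reason that supports it. If the general sentence in Section 4.7 is meant to govern, then 4.7.2.2, 8.13 and Table 24 should say so, and Table 12 should not say the opposite. Separate specifications that no one outside the sponsor can see do not replace the SAP text.

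**Conclusion.** The concern holds. As written, the SAP omits an analysis that Protocol 8.4.3.2 requires: DKA events, serious or not, by treatment at onset over the 52 weeks, with exposure-adjusted rates. The Table 12 reason does not justify a limit by seriousness.

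The consequence is narrow. It concerns non-serious DKA in placebo children after a switch to dapagliflozin, in about 1-5% of placebo-arm time if 10-40% of placebo children enter the third randomisation, and less if fewer do. The documents give no DKA count, so whether any event is affected is unknown. The 26-week and up-to-Week-32 comparisons are unaffected. This should be corrected because it concerns a named risk and a stated safety objective, not because a large shift is expected.

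**What to change.** In SAP 4.7.2.2, Appendix 8.13 and Table 24, add one ST+LT table of all DKA events sent for adjudication, serious or not, by adjudication category and treatment received at onset, with the exposure-adjusted rates of Section 3.4.1. Delete the DKA row from Table 12, which would then be untrue, so that the SAP agrees with itself and with Protocol 8.4.3.2.

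Two optional clarifications: a footnote on the first-treatment ST+LT table that the placebo column includes children switched to active drug, and an explicit mention in 4.7.2.2 of the up-to-Week-32 DKA table.

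The cost is SAP wording and one table. The at-onset rate is already defined and is already used for AEs, SAEs and marked laboratory abnormalities.

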4.7.2.3 Cardiovascular and hepatic adjudicated events

Cardiovascular and hepatic events sent for adjudication will be listed only.

4.7.2.4 Hypoglycaemia

Hypoglycaemic events will be included in summaries for the ST, ST+LT and randomised withdrawal periods if their onset falls between the start of IP treatment and the cut-off dates defined for each period in [Table 8](#). The primary analysis will be based on data including

hypoglycaemia events occurring prior to rescue medication initiation; sensitivity analyses will include data after rescue medication initiation.

The number and proportion of subjects with hypoglycaemic events (including those reported as SAEs) will be tabulated in each treatment group by ADA and ISPAD categories (see Section 8.9) for:

- The ST period and the combined ST+LT period, prior to rescue medication initiation (as primary analyses).
- The ST period and the combined ST+LT period, regardless of rescue medication initiation (as sensitivity analyses).
- The combined ST+LT period, up to Week 32, prior to rescue medication initiation (as primary analyses).
- The combined ST+LT period, up to Week 32, regardless of rescue medication initiation (as sensitivity analyses).
- The randomised withdrawal period. The events, with a date onset occurring on or after the randomised withdrawal prior to rescue medication initiation, will be summarised separately for the three treatment comparisons described in Section 4.1.5 using the Randomised Withdrawal Subjects Data Set.

The ST+LT period prior to rescue medication initiation analysis will also be repeated for the subgroup of subjects on a stable baseline dose of metformin IR or XR (with or without insulin).

Hypoglycaemic events that do not fulfil the ADA or ISPAD categories will be presented as ‘Not classified’.

All information (symptoms, risk factors etc.) collected in the separate CRF pages for hypoglycaemic events (whether or not they fulfilled SAE criteria) will be summarised by treatment group and listed for the ST+LT period. For the ST+LT + Week 104 period, the listing will include all data collected up to Week 104.

Hypoglycaemic events meeting SAE criteria will also be presented in the listing.

